The index date was defined as the date of first occurrence of GCA code and cases were considered being incident if the GCA code first occurred after a minimal follow-up of 2 years. A treatment sequence was defined as the start of a new drug or the resumption of the same drug after a stop of drug dispensing ≥ 3 months. Annual incidence rates were calculated for the period 2009 to 2015 by using the people recorded in the EGB database as denominator.

Briefly, the results were the following: among the 752,717 patients recorded in the EGB database, 241 people fulfilled inclusion criteria with a mean follow-up of 3.7 (± 2.6) years. Annual incidence was ranging between 7 and 10/100,000 people ≥ 50 years-old that is 2300 patients/year. Demographic analyses showed that 72% of the patients were females and that mean age was 77.5 (± 8.9) years. 74.3% of the patients had at least one proxy (i.e ICD-10 code or a treatment) for hypertension, 39.4% for depression/insomnia and 33.6% for osteoporosis. After index date, temporal artery biopsy (TAB) was performed in 43.2%, high-resolution color Doppler ultrasound in 35.3% and 18FDG-positron emission tomography (PET) in 11.6%.

Regarding treatments, 84.3% of the patients used only GCs while 16.7% also received 1 to 3 adjunctive medications, mainly MTX. Mean 1st GCs sequence duration was 17.2 months (± 16.5) in 96.6% of the patients.

EGB database strengths included comprehensive patient demography, epidemiology, diagnostic methods and treatment sequences. In contrast, limited data were available for comorbidities (as only proxies were described), clinical presentations (cranial, polymyalgia rheumatica [PMR], extracranial), clinical forms (relapsing, GCs-dependant), doses of GCs used, cumulative GCs doses and GCs associated toxicities. In addition, patient journey was poorly described given that patients may be first seen by a variety of physicians according to their first signs and symptoms (e.g. ophthalmologist for blurred vision, neurologist for headache, etc.), data which was not available in the EGB database analysis.

The proportions of use of TAB, Ultrasound or PET have also to be confirmed as they thought to be unusually performed in the EGB analysis.

We propose to conduct an observational study aiming to describe GCA management and patient characteristics in France.

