7 STATISTICAL METHODS

7.1 Rationale for the number of patients and physicians

7.1.1 *Number of patients required*

Not applicable in a descriptive observational study

7.1.2 *Number of physicians*

Not applicable

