The following endpoints will be described overall and by type of patient (prevalent/incident), by time between signs/symptoms and diagnosis (qualitative variable), and by type of physicians who follows the patient:

- » GCA duration
- » Initial presentation: proportions of patients with cranial GCA, PMR, extracranial GCA, ESR/CRP, general signs
- » Clinical form
 - Proportion of patients with relapse and number of relapse,
 - Proportion of patients with recurrence and number of recurrences,
 - Dose of GCs-dependence
 - Proportion of patients with GCA complications.

Analysis of potential factors associated to relapse will be performed using logistic regression. The associated factors will be defined in the SAP.

- » GCA activity
 - Proportions of each clinical signs/symptoms of GCA activity

- Scores of the patient and physician global arteritis activity VAS (quantitative variable)

The concordance between the scores of the patient and physician global arteritis activity VAS will be evaluated using the kappa coefficient.

The potential factors associated with the increase of the global arteritis activity will be studied.

Description of the health status of GCA patients

» SF-36 questionnaire

The SF-36 is a self-report, 36 item survey measuring health-related quality-of-life. The SF-36 consists of eight scaled scores. A score ranging from 0 (indicating the worse health status) to 100 (indicating the best health status) is assigned for each domain. Scores and missing data of the SF-36 were handled according to the user's manual. The score for each item of SF-36 will be presented (in quantitative) as well as the total score for each domain.

» EQ5D-3L questionnaire

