3.5 Patient selection

3.5.1 Patient selection method

Physicians will start patient inclusion only when the study is initiated at their site and when all regulatory authorisations are obtained.

It is expected that 300 patients (prevalent or incident cases) will be recruited in this study. Based on the previous EGB database analysis, there are 2300 incident patients/year in France. Thus, including 300 incident and prevalent patients during the recruitment period, even excluding summer holidays, seems realistic

Each physician will be requested to include consecutively during the inclusion period all the patients meeting the eligibility criteria listed below and accepting to participate in the study.

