 - IV bolus dose (mg)
 - Switch PO dose (mg/day)
 - Cumulative dose according to investigator (mg)
 - Proportion of kinetics for which a corticotherapy for GCA (Horton) care has restarted after the kinetic
 - Proportion of patients with at least one GCA complication
 - Proportion of patients with ongoing specific treatment(s) for GCA complications

Current and/or past GCA complications according to the investigator judgment will be coded using the medical dictionary MedDRA®. They will be described by SOC and PT overall and by type of physicians who follows the patient.

To determine the potential factors associated to relapse, a logistic regression will be used. The outcome variable will be relapse (Yes/ No). First, a univariate analysis will be conducted. All significant

factor at the 20% threshold will be selected for a multivariate analysis. A backward elimination procedure will be used with a threshold of 5%.

The associated factors that will be studied are:

- Age (in classes)
- Gender (Male/Female)
- BMI at diagnosis (in classes)
- Smoking status (Smoker/ Former smoker/ Non-smoker ever / Unknown)
- Type of patient (Prevalent or incident)
- Physician who referred the patient (General practitioner/ Ophthalmologist / Neurologist/ Emergency/ Internist/ Rheumatologist/Other),
- Patient considered with late diagnosis by the physician who referred him (Yes/ No)
- Patient considered with late diagnosis according to calculated time interval between the first medical events related to GCA and diagnosis : (Yes/No)
- Patient with at least one cranial GCA symptom at diagnosis (Yes/No),
- Patients with at least one PMR symptom at diagnosis (Yes/No),
- Patient with at least one extracranial GCA symptom at diagnosis (Yes/No),
- Patient with abnormal value of ESR at diagnosis (ESR>50 mm/h)
- Patient with abnormal value of CRP at diagnosis (CRP> 25 mg/L) (Yes/No),
- Patient with fever (>38°C) at diagnosis (Yes/No),
- Patient with weight loss at diagnosis (Yes/No),
- Patient with alteration of the general condition at diagnosis (Yes/No),
- Patient has taken at least one immunosuppressant since diagnosis (Yes/No)
- Patient has taken at least one targeted biological therapy since diagnosis (Yes/No)
- Patient has taken at least one other long-term treatment for the medical care of GCA since diagnosis (Yes/No)
- VAS score (global arteritis activity) by patient (>50mm/≤50mm)
- VAS score (global arteritis activity) by physician (>50mm/≤50mm)
- Cumulative dose of GCs (mg)

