- GCA activity

- Scores of the physician global arteritis activity VAS will be analysed as quantitative variables and in classes (≤ 50 ; > 50 mm).
- Scores of the patient global arteritis activity VAS will be analysed as quantitative variables and in classes (≤ 50 ; > 50 mm).

The VAS scores of physician and patient will be divided into classes. The same cut-off (≤ 50 ; > 50 mm) for the two scores will be defined by CHUGAI according to their medical relevance.

In this case, the concordance between the scores of the patient and physician global arteritis activity VAS will be evaluated using the kappa K coefficient, which will be interpreted as follows:

- $K < 0.0$: No match
- $0.0 \leq K \leq 0.2$: Poor agreement
- $0.2 < K \leq 0.4$: Fair agreement
- $0.4 < K \leq 0.6$: Moderate agreement
- $0.6 < K \leq 0.8$: Good agreement
- $K > 0.8$: Very good agreement

To evaluate the GCA activity, the score of the physician global arteritis activity VAS will be used. For this score a threshold value = 10 mm was defined and validated by CHUGAI.

Patients with physician's VAS score less than or equal to 10 mm will be considered with "non-active GCA", while patients with physician's VAS score greater than 10 mm will be considered with "active GCA".

In this case, the potential associated factors with the increase of the GCA activity will be studied by logistic regression.

The outcome variable will be GCA (active/ Non-active). First, a univariate analysis will be conducted. All significant factor at the 20% threshold will be selected for a multivariate analysis. A backward elimination procedure will be used with a threshold of 5%.

The associated factors that will be studied are:

- Age (in classes)
- Gender (Male/Female)
- BMI at diagnosis (in classes)
- Smoking status (Smoker/ Former smoker/ never smoker/unknown)
- Prevalent or incident patient,
- Physician who referred the patient,
- Patient considered with late diagnosis by the physician who referred him (Yes/ No)
- Patient with at least one cranial GCA symptom at diagnosis (Yes/No),
- Patients with at least one PMR symptom at diagnosis (Yes/No),
- Patient with at least one extracranial GCA symptom at diagnosis (Yes/No),
- Patient with abnormal value of ESR (ESR>50 mm/h) at diagnosis
- Patient with abnormal value of CRP (CRP> 25 mg/L) at diagnosis (Yes/No),
- Patient with fever at diagnosis (Yes/No),
- Patient with weight loss at diagnosis (Yes/No),

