5.5.4.2 Description of patients

The following patients' characteristics will be described overall and by type of physician who follows the patient:

- Type of the patient's visit (Outpatient visit/Day hospital/ In-patient hospitalization)
- Age (years) as quantitative variable and in classes ([50 ; 70[/ ≥ 70) ([APPENDIX](#))
- Gender
- Weight at diagnosis (kg)
- Weight at inclusion (kg)
- Height at diagnosis (cm)
- Body mass index (BMI) (kg/m²) at diagnosis ([APPENDIX](#))
- BMI in classes (kg/m²) (<18.5 / [18.5 ; 25[/ [25.0 ; 30[/ ≥ 30) at diagnosis
- Smoking status (Smoker/ Former smoker/ Non-smoker ever / Unknown)
- Significant medical and surgical history and comorbidities (excluding those related / aggravated by the use of glucocorticoids according to the investigator's judgment and complications related to GCA (Horton) according to the investigator's judgment

- Significant medical and surgical history and comorbidities overall by MedDRA System Organ Class (SOC) and Preferred Term (PT)
- Significant medical and surgical history and comorbidities presented before the GCA (HORTON) diagnosis
- Significant medical and surgical history and comorbidities with ongoing specific treatment(s)

A listing of other significant medical and surgical history and comorbidities (excluding those related / aggravated by the use of glucocorticoids according to the investigator's judgment and complications related to GCA (Horton) according to the investigator's judgment) will be presented.

- Treatments administered by the patients at/after diagnosis of GCA (Horton)
 - Proportion of patients taking at least one treatment of Antiplatelets
 - Proportion of patients taking at least one treatment of Statins
 - Proportion of patients taking at least one treatment of Antiosteoporotic
 - Proportion of patients taking at least one treatment of Antihypertensives
 - Proportion of patients taking at least one treatment of Antidiabetics
 - Proportion of patients taking at least one treatment of Inhibitors of the proton pump
 - Proportion of patients taking at least one treatment of Hypnotics
 - Proportion of patients taking at least one treatment of Antidepressants
 - Proportion of patients taking at least one other treatment

- Concomitant treatments administered by the patients at diagnosis of GCA (Horton)
 - Proportion of patients taking at least one treatment of Antiplatelets
 - Proportion of patients taking at least one treatment of Statins

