Rheumatologist		
Other		
Patient considered with late diagnosis by the physician who referred him		
No (reference)		
Yes		
Patient considered with late diagnosis according to time between first symptom and diagnosis		
No (reference)		
Yes		
Patient with at least one cranial GCA symptom at diagnosis		
No (reference)		

Table 22 - Efficacy analysis – Univariate analysis* of the effect of the patients characteristics on the relapse (outcome variable : at least one relapse / no relapse) – Analysis population (N=XX)

Parameter	OR [CI 95%]	pvalue
Yes		
Patient with at least one PMR symptom at diagnosis		
No (reference)		
Yes		
Patient with at least one extracranial GCA symptom at diagnosis		
No (reference)		
Yes		
Patient with abnormal value of ESR at diagnosis (ESR>50 mm/h)		
No (reference)		
Yes		
Patient with abnormal value of CRP at diagnosis (CRP> 25 mg/L)		
No (reference)		
Yes		
Patient with fever (> 38°C) at diagnosis		
No (reference)		
Yes		
Patient with weight loss at diagnosis		
No (reference)		
Yes		
Patient with alteration of the general condition at diagnosis		
No (reference)		
Yes		
Patient has taken at least one immunosuppressants since diagnosis		
No (reference)		
Yes		
Patient has taken at least one targeted biological therapy since diagnosis		
No (reference)		
Yes		
Patient has taken at least one other long-term treatment since diagnosis		
No (reference)		
Yes		
VAS score of the patient		
<50 mm (reference)		
>50 mm		

Table 22 - Efficacy analysis – Univariate analysis* of the effect of the patients characteristics on the relapse (outcome variable : at least one relapse / no relapse) – Analysis population (N=XX)

Parameter	OR [CI 95%]	pvalue
VAS score of the physician		
≤ 50 mm (reference)		
>50 mm		
Cumulative dose of GCs (or in classes that will be defined according to the distribution of this variable)		

PMR : PolyMyalgia Rheumatica
 ESR : Erythrocyte Sedimentation Rate
 CRP : C Reactive Protein
 OR : Odd ratio
 CI : Confidence interval
 VAS : Visual Analog Scale
 GCs : GlucoCorticoids

*Univariate logistic regression
 The percentages are calculated compared to filled data
 STUDY : CHUGAI-ARTEMIS - Edition date: DDMMYY
 Pgm : EFFICACY\GCA.SAS

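### Both exploratory regressions put measured factors into classes; on the protocol's own age figures the cut at 70 alone gives up about half the information on a linear age effect

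*SAP*

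**What the plan says.** SAP 5.5.2 plans two logistic regressions, one for relapse (Tables 22-23) and one for active disease (Tables 26-27). In each, factors are screened one at a time at 20% and then removed backwards at 5%.

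- **Age** is listed as "Age (in classes" in both. SAP 5.5.4.2 gives the classes and shows that the value itself is available: "Age (years) as quantitative variable and in classes ([50 ; 70[/ ≥ 70".
- **BMI** enters both models in four classes, **ESR** as above 50 mm/h or not, **CRP** as above 25 mg/L or not, and **calculated diagnostic delay** as late or not. ESR and CRP values are summarised in Table 15, and delay in months is described as a quantity in SAP 5.4.
- **Cumulative glucocorticoid (GC) dose** is listed without classes in the SAP 5.5.2 text, but the shells of Tables 22 and 26 read "Cumulative dose of GCs (or in classes that will be defined according to the distribution of this variable".
- **VAS as a factor** appears in the relapse model only: patient and physician scores are each cut at 50 mm.
- **VAS as an outcome** appears in the activity model only, using the physician score: "For this score a threshold value = 10 mm was defined and validated by CHUGAI".

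The documents give no reason for using the age, ESR or CRP cuts inside the models. On sample size, SAP 3.5.1 says "It is expected that 300 patients (prevalent or incident cases) will be recruited in this study", and Protocol 7.1.1 gives the rationale as "Not applicable in a descriptive observational study".

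**The concern.** Cutting a measured factor in two treats everyone on one side of the cut as alike and patients just either side of it (69 and 71 years, ESR 49 and 51) as different. If the association is gradual, this discards information. An unbalanced cut discards more, and the mean age in the earlier cohort lies well above 70. The loss acts twice, because a weakened factor can fail the 20% screen and never reach the multivariable model. A retained factor that is coarsely coded also adjusts less well for confounding.

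The shell wording on GC dose leaves a modelling choice open until the data have been seen. These regressions are the plan's only analyses of associated factors, so what is at stake is missed or imprecise associations.

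**Working it through.** The plan states no power or information figure, so there is none to reproduce.

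**Inputs.** Mean age 77.5, SD 8.9 (claims-database cohort, Protocol section 1, used as a proxy for this study); cut at 70 (SAP 5.5.4.2); N = 300 (SAP 3.5.1); thresholds of 20% and 5% (SAP 5.5.2). Assumed, because the documents do not give them: a 35% outcome, an odds ratio of 1.4 per 10 years, and an effect linear on the logit scale.

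**1. Information kept by the age cut.** For a normal variable cut at standardised point c, with share p below it, the fraction kept is φ(c)² / [p(1−p)].
- c = (70 − 77.5) / 8.9 = −0.843
- p = Φ(−0.843) = 0.200
- φ(−0.843) = 0.2797, so the fraction kept is 0.0782 / (0.1997 × 0.8003) = 0.49
- Equivalent sample size: 300 × 0.4895 ≈ 147

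With a normal truncated at 50 the loss is again 51%. With a beta shape on 50-100 with the same mean and SD it is 46%. The loss is therefore 46% to 51%.

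**2. Power.**
- Effect per SD: ln(1.4) × 0.89 = 0.299
- Noncentrality, continuous: √(300 × 0.35 × 0.65) × 0.299 = 2.47
- Noncentrality, cut: 2.47 × √0.4895 = 1.73
- Approximate power at 5%: Φ(2.47 − 1.96) = 70% against Φ(1.73 − 1.96) = 41%
- Simulated logistic fits, repeated with different seeds: 67% to 68% continuous against 34% to 38% cut
- Passing the 20% screen, simulated: about 88% against about 65%

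**3. The other variables.** No distribution is given, so only conditional figures are possible:

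| Variable | Assumption | Information lost |
|---|---|---|
| ESR or CRP, two classes | normal, split 50/50; 20/80; 10/90 | 36%; 51%; 66% |
| ESR or CRP, two classes | lognormal (log-SD 0.5-1.0), linear on raw scale, 10-90% below the cut | 39% to 95% |
| BMI, four classes | mean 25-27, SD 4-5 | 14% to 16% |
| GC dose, if put in quartiles | normal; lognormal (log-SD 0.5-1.0) | 14%; 25% to 53% |
| GC dose, if kept continuous | none needed | 0% |
| Physician VAS outcome, cut at 10 mm | proportional odds, few ties, 50%; 20% or 80% active | 25%; 52% |

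The VAS row uses 1 − 3p(1−p), with p the share active: 1 − 3 × 0.25 = 0.25 and 1 − 3 × 0.16 = 0.52.

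**The case against.** The strongest reply is that these are secondary, exploratory models in a descriptive study with no power claim. Prespecified classes that the SAP labels abnormal are easy to read, and if risk really changes at the cut, nothing is lost. All of that stands. It limits the weight of the point, but no document claims a threshold effect for age, ESR or CRP, and keeping the classes in the descriptive tables preserves readability.

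A reader might also infer several stronger things that the documents do not support:

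- **That a single range of loss applies to every cut.** Only age has a documented distribution, and the table above shows how far the others move with the assumption. Adding the claims cohort's mean follow-up of 3.7 years to age would leave about 10% below 70 and 35% of the information. But that figure is database follow-up, not disease duration in a sample that includes newly diagnosed patients.
- **That the 10 mm cut runs through both regressions.** It defines the outcome of the activity model only; the relapse model cuts VAS at 50 mm, as a factor.
- **That GC dose will be classed, or classed to suit the result.** Classes are an alternative in two table shells, and they would follow the distribution of the dose, not the outcome. The fault is only that the choice is left open.
- **That the 10 mm outcome contradicts the protocol**, which says "The potential factors associated with the increase of the global arteritis activity will be studied". The protocol names no scale or model for this, a single visit cannot show a within-patient increase, and the SAP also summarises the VAS as a quantity. An ordinal model is an addition, not a correction. With many scores at exactly zero its advantage would be smaller than shown.
- **That age at inclusion is the wrong age.** The activity outcome is measured at inclusion, so that choice is defensible there.
- **That a per-mg odds ratio will print as 1.00.** SAP 5.1 leaves the decimals of derived data open, so this is a template detail.

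**Conclusion.** The point holds as a cheap improvement. Age, BMI, ESR, CRP and calculated delay enter both regressions as classes although the values are collected, and the shells leave the form of GC dose open. For age the cost is about half the information (46% to 51%), if ages resemble the claims-database cohort and the effect is roughly linear. The drop in power from about 67% to about 35% further assumes the stated odds ratio and outcome rate. For the other variables the size of the loss cannot be established from the documents. The consequence is missed or imprecise factors and weaker adjustment in secondary models; the primary objective is unaffected.

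**What to change.** In SAP 5.5.2 and the shells of Tables 22-23 and 26-27:

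- Enter age (per 10 years), BMI (per 5 kg/m²), ESR (per 10 mm/h) and log2 CRP as continuous terms, with a 3-knot spline prespecified as the linearity check.
- Enter cumulative GC dose per 1,000 mg and delete the shell wording that allows classes based on its distribution.
- Keep the 10 mm logistic model for activity and add a cumulative-logit analysis of the physician VAS as a sensitivity analysis.
- Keep all classes in the descriptive tables.

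Calculated delay can stay classed: it is a difference of month-and-year dates, with missing months imputed (SAP 5.2.2 and section 8), so it is coarse already.

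The cost is SAP wording and model code, with no new data. The downside is that odds ratios are reported per unit rather than per clinical class. Continuous coding of GC dose also does not settle how to interpret it in the relapse model, since relapses are themselves treated with glucocorticoids.

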1 INTRODUCTION AND RATIONALE FOR THE STUDY

Giant cell arteritis (GCA) - also known as temporal arteritis, cranial arteritis, or Horton's disease - is a form of immune-mediated inflammatory systemic vasculitis that affects large and medium-sized arteries, predominantly affecting the extracranial branches of the carotid arteries and the subclavian and axillary branches of the aorta (Zöller et al. 2013). GCA may present with systemic symptoms such as fever, but the most common symptom is temporal and occipital headache accompanied by scalp tenderness (Babigumira et al. 2017). The arterial blockage associated with GCA leads to ischemic symptoms such as jaw claudication, intermittent claudication of the tongue and muscles involved in swallowing, and rarely infarction of the scalp or the tongue (Babigumira et al. 2017).

GCA causes significant complications, particularly vision loss (4% for patients with large-vessel GCA and 11% for those with cranial disease (Muratore et al. 2014). GCA patients are also 17.3 times (95% CI, 7.9 to 33.0) more likely to develop thoracic aortic aneurysm and 2.4 times (95% CI, 0.8 to 5.5) more likely to develop isolated abdominal aortic aneurysm (Evans, O'Fallon, et Hunder 1995).

The mainstay of GCA clinical management is initiation of high-dose glucocorticoids (GCs), typically prednisone from 0.7 to 1mg/kg/day (PNDS 2017) maintained and tapered gradually. In most patients, the administration of high-dose GCs is followed by a rapid improvement of systemic inflammatory signs, presumably due to the effective suppression of interleukin-6 and the acute-phase response. In current practice, the tapering of GCs is generally started once reversible clinical signs have abated and laboratory values have been normalized. The dose of prednisone is initially reduced by 10 to 20% every 2 weeks; once the dose falls below 10 mg per day, tapering is usually slowed (generally by 1 mg per month). These recommendations match those developed by the British Society for Rheumatology (BSR) (Dasgupta et al. 2010) and by the French study group for Large Vessel Vasculitis (GEFA) (Bienvenu et al. 2016a). Guidelines from the European League Against Rheumatism (EULAR) suggest a faster initial tapering to a dose of 10 to 15 mg per day within 3 months after treatment initiation (Mukhtyar et al. 2009).

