5.5 Analyses of secondary objectives

The analysis of the secondary objectives will be also performed on the analysis population.

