9.3.2 Description of GCA characteristics

Table 14 - Efficacy analysis – Description of GCA characteristics - Analysis population (N=XX)

Parameter	Statistics	Total (N=XX)
Time between diagnosis and inclusion (months)	Mean SD Median [Q1 ; Q3] [Min ; Max] Filled, n(%) Missing, n(%)	
Type of patient * Incident Prevalent	n(%) n(%) Filled, n(%) Missing, n(%)	

*Incident if diagnosis of GCA ≤6 weeks from inclusion
Prevalent if diagnosis of GCA >6 weeks from inclusion
The percentages are calculated compared to filled data
STUDY : CHUGAI-ARTEMIS - Edition date: DDMMYY
Pgm : EFFICACY\GCA.SAS

Table 15 - Efficacy analysis – Initial presentation of GCA - Analysis population (N=XX)

Parameter	Statistics	Total (N=XX)
Patient with at least one cranial manifestation at diagnosis No Yes	n(%) n(%) Filled, n(%) Missing, n(%)	
Cranial manifestation* Headaches Scalp sensitivity Anomalies of the temporal arteries Ischemia-related vision impairment and-or loss Mouth pain or jaw claudication during mastication Ischemia-related vision impairment and-or loss Stroke or transient ischemic attack (TIA) Other	n(%) n(%) n(%) n(%) n(%) n(%) n(%) n(%)	
Patient with at least one PMR symptom at diagnosis No Yes	n(%) n(%) Filled, n(%) Missing, n(%)	
PMR symptom * Morning stiffness and-or pain in the shoulder girdle Morning stiffness and-or pains in the pelvic girdle Inflammatory arthromyalgia Peripheral arthritis/ Other	n(%) n(%) n(%) n(%) n(%)	
Patient with at least one extracranial event (excluding PMR) at diagnosis No Yes	n(%) n(%) Filled, n(%) Missing, n(%)	
Extracranial event (excluding PMR)* Thoracic or abdominal aortic aneurysm and-or dilatation Aortitis and-or involvement of aortic branch(s) in imaging Angina and-or Myocardial infraction Claudication of an upper limb and-or claudication of a lower limb Sign of subclavian stenosis	n(%) n(%) n(%) n(%) n(%)	

Table 15 - Efficacy analysis – Initial presentation of GCA - Analysis population (N=XX)

Parameter	Statistics	Total (N=XX)
Other	n(%)	
Value of ESR (mm/1st h) at diagnosis	Mean SD Median [Q1 ; Q3] [Min ; Max] Filled, n(%) Missing, n(%)	
Value of ESR (mm/1st h) at diagnosis in classes ≤50 mm/h >50mm/h	n(%) n(%) Filled, n(%) Missing, n(%)	
Value of ESR (mm/1st h) at inclusion	Mean SD Median [Q1 ; Q3] [Min ; Max] Filled, n(%) Missing, n(%)	
Value of ESR (mm/1st h) at inclusion in classes ≤50 mm/h >50mm/h	n(%) n(%) Filled, n(%) Missing, n(%)	

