Kinetics for which a corticotherapy for GCA (Horton) care has restarted after the kinetic No Yes	n(%) n(%) Filled, n(%) Missing, n(%)	

IV : Intravenous PO : Per Oral

The percentages are calculated compared to filled data

STUDY : CHUGAI-ARTEMIS - Edition date: DDMMYY

Pgm : EFFICACY\GCA.SAS

Table 20 - Efficacy analysis – Clinical Form - GCA complications - Analysis population (N=XX)

Parameter	Statistics	Total (N=XX)
Patient with at least one GCA complication		
No	n(%)	
Yes	n(%) Filled, n(%) Missing, n(%)	
If yes, Patient with ongoing specific treatment(s) for GCA complications		
No	n(%)	
Yes	n(%) Filled, n(%) Missing, n(%)	

The percentages are calculated compared to filled data
STUDY : CHUGAI-ARTEMIS - Edition date: DDMMYY
Pgm : EFFICACY\GCA.SAS

Table 21 - Efficacy analysis – Complications related to GCA according to the investigator's judgment by MedDRA SOC and PT – Analysis population (N=XX)

System Organ Class	Preferred Term	Total (N=XX)	
		# Patients (%)	# Comps (%)
Patients with at least one complication related to GCA			
Number of complications related to GCA			
SOC1			
	PT1.1		
	PT1.2		
	...		
SOC2			
	PT2.1		
	PT2.2		
	...		
...			

Study: CHUGAI-ARTEMIS - Edition date: DDMMYY
Pgm : EFFICACY\COM.SAS

Patients (%): Number of patients (percentages with number of patients as reference)

Comps (%): Number of complications (multiple occurrences of the same complication in one patient are counted multiple times) (percentages with number of complications as reference)

This table will be presented also by type of physicians who follows the patient.

Table 22 - Efficacy analysis – Univariate analysis* of the effect of the patients characteristics on the relapse (outcome variable : at least one relapse / no relapse) – Analysis population (N=XX)

Parameter	OR [CI 95%]	pvalue
Age in classes		x.xxxx
[50 – 70[(reference)	1.00	
≥ 70 years	X.XX [X.XX ; X.XX]	
Gender		...
Male (reference)	...	
Female	...	
BMI in classes (kg/m²)		
Normal (BMI between [18.5-25]) (reference)		
Under weight (BMI <18.5)		
Over weight (BMI between [25.0 ; 30])		
Obesity (BMI ≥ 30)		
Smoking status		
Non-smoker ever (reference)		
Former smoker		
Smoker		
Unknown		
Type of patient		
Prevalent (reference)		
Incident		
Physician who referred the patient		
General practitioner (reference)		
Ophthalmologist		
Neurologist		
Emergency		
Internist		

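### The relapse model pools patients diagnosed within the last 6 weeks with long-followed patients and enters incident/prevalent as a factor with no term for time at risk, so that odds ratio mainly reflects length of follow-up and may not be estimable

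*SAP*

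**What the plan says.** SAP 5.5.2 looks for factors associated with relapse by logistic regression: "The outcome variable will be relapse (Yes/ No", that is, any relapse up to the single study visit. Section 5.5 sets the population: "The analysis of the secondary objectives will be also performed on the analysis population". That population mixes newly diagnosed and established cases ("It is expected that 300 patients (prevalent or incident cases) will be recruited in this study", SAP 3.5.1). The Table 14 footnote defines the first group: "Incident if diagnosis of GCA ≤6 weeks from inclusion".

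The candidate list contains "Type of patient (Prevalent or incident", and Table 22 sets the reference level as "Prevalent (reference", so the reported odds ratio is for incident patients. Selection has two stages: each significant "factor at the 20% threshold will be selected for a multivariate analysis", followed by backward elimination at 5%. The SAP does not say whether significance is judged by a Wald, score or likelihood-ratio test, and it has no rule for an empty cell.

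Time between diagnosis and inclusion is derived (SAP Appendix, item 3) and described in Table 14, but it is not in the relapse factor list. Three factors in that list are defined by what has happened since diagnosis: at least one immunosuppressant, at least one targeted biologic, and at least one other long-term treatment. Cumulative glucocorticoid dose also builds up over that period.

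**The concern.** Ever-relapse depends on how long the patient has been observed. A patient in week 3 and a patient in year 3 have very different opportunities to be counted as a relapser, and the model has no term for this. The incident/prevalent factor is a coarse stand-in for follow-up. Reported as an associated factor, it would say only that patients observed for longer have relapsed more often.

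Two further problems follow. First, the incident group may contain no relapse at all. The likelihood then has no finite maximum for this factor, and what Table 22 shows depends on the fitting algorithm and the test chosen. Second, if the factor is screened out, the incident patients remain as non-relapsers who have also had little time to collect treatments or cumulative dose. That alone produces a positive association between those factors and relapse.

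**Working it through.** **Inputs from the documents.** 300 patients (SAP 3.5.1); 2300 incident cases a year in France (SAP 3.5.1); about 2600 listed physicians and 150 active ones (SAP 3.4); recruitment of 3 months (SAP 3.3) or 5 months (protocol 3.3). The plan gives no figure to reproduce: protocol 7.1 offers no sample-size calculation, and neither document gives an incident share or a relapse rate.

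**Assumptions, not in the documents.** Incident cases are spread evenly over the listed physicians; relapse risk within 6 weeks is 0.5-2% (3% as a sensitivity value); relapse among prevalent patients is 20-40%; 20% of prevalent patients and no incident patient use the example treatment.

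**Step 1. Size of the incident group.** 2300 × 3/12 × 150/2600 = 33, and 2300 × 5/12 × 150/2600 = 55. That is 11-18% of 300.

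**Step 2. Chance of an empty incident cell**, (1 − p)^n:

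| 6-week risk p | n = 33 | n = 45 | n = 55 |
|---|---|---|---|
| 0.5% | 85% | 80% | 76% |
| 1% | 72% | 64% | 58% |
| 2% | 51% | 40% | 33% |
| 3% | 37% | 25% | 19% |

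**Step 3. An empty cell: 0/45 incident and 102/255 prevalent relapsed.** The log odds ratio diverges as the iterations proceed. Stopped at 8, 12 or 15 Newton iterations, the Wald p is 0.55, 0.91 or 0.97, which fails the 20% screen each time. The likelihood-ratio statistic is 2 × {[102 ln 0.40 + 153 ln 0.60] − [102 ln 0.34 + 198 ln 0.66]} = 2 × (−171.62 + 192.31) = 41.4 on 1 df, p about 1e-10, which passes. Adding 0.5 to each cell (equal to Firth for a single binary factor) gives a finite odds ratio: (0.5/45.5)/(102.5/153.5) = 0.016.

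**Step 4. One incident relapse: 1/45 against 102/255.** The odds ratio is (1/44)/(102/153) = 0.034, with standard error of the log √(1 + 1/44 + 1/102 + 1/153) = 1.02, 95% CI 0.005 to 0.25 and Wald p 0.0009. The factor is estimable and passes the screen under either test.

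**Step 5. Bias if the factor is dropped.** Take I incident patients with no relapse and no use of the treatment, and P = 300 − I prevalent patients of whom a fraction r have relapsed. Let 20% of the prevalent patients use a treatment unrelated to relapse. Users have relapse odds r/(1 − r). Non-users have odds 0.8Pr / [0.8P(1 − r) + I]. The ratio is 1 + I/[0.8P(1 − r)].
- I = 33, r = 0.20: 1 + 33/(0.8 × 267 × 0.8) = 1.19.
- I = 55, r = 0.40: 1 + 55/(0.8 × 245 × 0.6) = 1.47.

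The true value within prevalent patients is 1.00.

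**The case against.** Much can be said for the plan.

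- **An empty cell is not assured.** Its probability rests on two assumed figures. The 150 active physicians are those who include at least one patient, so they are not average members of the list; more incident patients would make an empty cell less likely. At 3% risk the chance is only 19-37%. A reader might infer that the odds ratio is likely to be inestimable; the documents do not supply what that would need.
- **The SAP does not choose the Wald test.** It names SAS and a significance threshold only. A reader might infer that the software default will discard the strongest factor. That can happen, but only with an empty cell and a Wald-type screen. SAP 7.3 also requires review of warnings and nonsensical results, so a diverging estimate would probably be noticed. What remains is that no response is prespecified, so the remedy would be chosen after seeing the data.
- **Incident patients are not outside the risk set.** The protocol introduction describes current practice thus: "The dose of prednisone is initially reduced by 10 to 20% every 2 weeks". Reductions can therefore fall within 6 weeks, and Appendix item 5 handles relapse dates for incident patients. To say that they carry no information on relapse would also contradict an assumed risk of 0.5-2%. They have had little time, not none.
- **If the factor is kept with an empty cell, the other coefficients are unharmed.** Incident patients then drop out of the likelihood for everything else. In a simulated data set of 300 with 45 incident patients and no incident relapse, another factor's log odds ratio and standard error were 0.5669 and 0.2605 both in the full model and in prevalent patients alone. The bias in step 5 belongs to the univariate results and to a multivariable model that has lost the factor.
- **The analysis is exploratory and secondary**, in a study whose protocol plans no statistical testing. No primary endpoint is touched. That limits the weight of the point, but Tables 22-23 will still report odds ratios, confidence intervals and p-values.

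**Conclusion.** The point holds as a defect of time at risk. The relapse model mixes patients with at most 6 weeks of disease and patients with any longer duration, has no term for that difference, and offers the difference itself as an associated factor. This follows from the text and needs no assumption about numbers. Whether the factor is estimable (step 4) or not (step 3), its odds ratio mainly describes follow-up.

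The estimation failure is conditional. It occurs if no incident patient has relapsed: 33-85% under 33-55 incident patients and a 6-week risk of 0.5-2%, less at higher risk. In that case the unnamed test decides whether the factor survives the 20% screen. If it does not survive, an inert treatment that accumulates over time shows a crude odds ratio of 1.19-1.47 under the stated assumptions. This deserves correction before the model is run, but it does not threaten the study's main descriptive results.

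**What to change.** In SAP 5.5.2 and Tables 22-23:

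1. Fit the relapse model in prevalent patients only and delete the type-of-patient factor from its candidate list.
2. Force in time between diagnosis and inclusion, already derived in Appendix item 3. Restriction alone is not enough, because prevalent patients range from just over 6 weeks to years since diagnosis. Time to first relapse, from the month and year already collected, would be an alternative.
3. Name the likelihood-ratio test for both the 20% screen and the 5% elimination. If a factor has an empty cell, use Firth penalised likelihood with profile-likelihood confidence intervals.
4. Leave relapse in incident patients to the description by type of patient that SAP 5.5.2 already plans; nothing needs adding there.

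The cost is a change of wording and a few procedure options, with no new data. The model loses about 10-20% of patients (33-55 of 300 on the assumed split) and few or no relapses.
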